7.2 RELATIONSHIP TO THE INVESTIGATIONAL DEVICE

The investigator should assess the relationship of the adverse event to the investigational device. The relationship should be assessed using the categories presented in **Table 7.2-1**.

TABLE 7.2-1: RELATIONSHIP BETWEEN ADVERSE EVENTS AND INVESTIGATIONAL DEVICE

Definite	Definite relationship exists between the device and an adverse event
Probably Related	A reasonable causal relationship between treatment with the investigational device and an adverse event is more likely than not.
Possibly Related	A reasonable relationship exists between the device treatment and an adverse event, but the causal relationship is unclear or lacking.
Not Likely Related	A temporal relationship exists between the device treatment and an adverse event, but there is no reasonable causal relationship. For example the adverse event occurs in a time frame, which makes a causal relationship to device treatment improbable.
Unrelated	No relationship between treatment with the investigational device and the adverse event exists.

7.3 UNANTICIPATED ADVERSE DEVICE EFFECTS (EVENTS)

An unanticipated adverse device effect is defined as “any serious adverse effect on health or safety, or any life-threatening problem, or death caused by, or associated with, a device; if that effect, problem, or death was not previously identified in nature, severity, or degree of incidence in the investigational plan, or application (including supplementary application), or any other unanticipated serious problem associated with a device that relates to the rights, safety, or welfare of subjects.”

If an unanticipated adverse device effect occurs, the investigator should promptly notify the Sponsor of such an event, preferably within 48 hours of learning of the event. The investigator must promptly notify the reviewing IRB of such an event as soon as possible, but no later than 10 working days after learning of the event.

7.4 SERIOUS ADVERSE EVENT

Each adverse event should be assessed for its seriousness. The definition below should be used for this assessment. Please note that the term serious adverse event is not synonymous with a “severe” adverse event, which may be used to describe the intensity of an event experienced by the subject. (Please refer to Section 7.6 for severity definitions.)

An adverse event should be classified as serious if it meets any of the following criteria:

- a. Death
Death was an outcome of the adverse event.
- b. Life-threatening
The subject was at substantial risk of dying at the time of the adverse event, or use or continued use of the device.
- c. Hospitalization (initial or prolonged)
Admission to the hospital or prolongation of hospitalization was a result of the adverse event.
- d. Disability or Permanent Damage
The adverse event resulted in a substantial disruption of a person's ability to conduct normal life functions, i.e., the adverse event resulted in a significant, persistent or permanent change,

- impairment, damage or disruption in the patient's body function/structure, physical activities and/or quality of life.
- e. Congenital Anomaly/Birth Defect
Exposure to a medical product prior to conception or during pregnancy may have resulted in an adverse outcome in the child.
 - f. Required Intervention to Prevent Permanent Impairment or Damage (Devices)
Medical or surgical intervention was necessary to preclude permanent impairment of a body function, or prevent permanent damage to a body structure, either situation suspected to be due to the use of a medical product.
 - g. Other Serious (Important Medical Events)
The event does not fit the other outcomes, but the event may jeopardize the subject and may require medical or surgical intervention (treatment) to prevent one of the other outcomes.

Non-serious adverse events are all events that do not meet the criteria for a "serious" adverse event.

7.5 REPORTING REQUIREMENTS FOR SERIOUS ADVERSE EVENTS

Serious adverse events must be reported to the Sponsor as soon as possible, preferably within 24 hours but in no event later than 72 hours. The adverse event must be recorded on the subject's study-specific data form. The Sponsor will conduct an investigation. If the Sponsor determines that the investigation presents an unreasonable risk to subjects, all investigations or parts of the investigation presenting that risk will be terminated as soon as possible. The investigator must report serious adverse events to the reviewing IRB according to the IRB regulations at the study site.

7.6 SEVERITY

Each adverse event should be assessed for its severity, or the intensity of an event experienced by the subject, using the following classifications:

- | | |
|--------------|-----------------------------------------------------------------|
| 1 = Mild | Discomfort noticed, but no disruption to daily activity |
| 2 = Moderate | Discomfort sufficient to reduce or affect normal daily activity |
| 3 = Severe | Inability to work or perform normal daily activity |

7.7 DEATHS

The investigator must notify the Sponsor as soon as possible, preferably within 24 hours but in no event later than 48 hours, of learning of a subject's death, regardless of whether the death is related or unrelated to the investigational device. The investigator should attempt to determine, as conclusively as possible, whether the death is related to the device. The cause of death and the investigator's discussion regarding whether or not the death was device-related should be described in a written report. The investigator must report death to the reviewing IRB according to the IRB regulations at the study site.

7.8 PRE-EXISTING CONDITIONS

A pre-existing condition should not be reported as an adverse event unless there has been a substantial increase in severity or frequency of the problem that has not been attributed to natural history.

8. RISK ANALYSIS

8.1 POTENTIAL RISKS

This treatment modality was designed to inherently minimize the risk to the subject. However, ultrasound exposure with subsequent heating of the soft tissue could involve the risks listed below:

TABLE 8.1.1: EXPECTED TREATMENT EFFECTS

Expected Treatment Effects	Duration
Bruising/Ecchymosis	Up to 2 weeks
Edema/Swelling	Up to 72 hours
Erythema/Redness	Up to 72 hours
Local Muscle Weakness/Paresis	Up to 6 weeks
Nodules	Up to 4 weeks
Acute Pain	Immediate/momentary (while energy is being delivered) - 2 hours
Skin Burn	Up to 4 weeks
Tenderness/Soreness/Pain/Sensitivity to Touch	Up to 2 weeks
Tingling/Paresthesia/Numbness/Nerve Related Transient Pain	Up to 6 weeks
Welting/Raised Areas of Edema	Up to 1 week

Common risks associated with Ibuprofen include nausea, diarrhea, dizziness, headaches and hypertension. NSAIDs (e.g., Ibuprofen) should not be given to patients who have experienced asthma, urticaria, or allergic-type reactions after taking aspirin or other NSAIDs.

These risks will be minimized or reduced by monitoring the subject during the treatment and observing the skin's response to receiving the treatment. If the treatment is not tolerated, the investigator must stop administering treatment for the subject's safety, and the subject will be followed for adverse events for 365 days.

Previous clinical studies with the Ulthera[®] System have shown that the sensory response was tolerable from the subject's and investigator's perspectives. The discomfort was transient and no subject had any residual pain beyond 30 minutes.

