
Exclusion Criteria:
	
 1. Presence of an active systemic or local skin disease that may affect wound healing. 2. History of Bell’s Palsy. 3. History of chronic or frequently recurring episodic (recurrent episode in past 12 months) autoimmune diseases such as Multiple Sclerosis, Crohn’s Disease, Psoriasis, Myasthenia Gravis, Lambert-Eaton Syndrome that has required immune suppressant therapy (such as biologic drug or corticosteroid treatment). 4. Palpable thyroid lesion, lymphadenopathy, or other pathological changes within the treatment area. 5. History of skin cancer in the areas to be treated, basal cell nevus syndrome, or jaw cysts. 6. Known allergy or sensitivity to Ibuprofen. 7. Severe solar elastosis. 8. BMI > 30. 9. Significant changes in weight (e.g. more than 5 pounds) over the past 6 months or anticipated significant changes in weight or diet over the course of the study.

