4.3 ELIGIBILITY

4.3.1 INCLUSION CRITERIA

Subjects must meet all of the following criteria for study enrollment:

1. Male or female, age 30 to 70 years.
2. Subject in good health.
3. BMI \leq 30.
4. Skin laxity in the area(s) to be treated as determined by trained physician assessors.
5. Willingness to avoid excessive or prolonged exposure to sunlight, tanning booths, sun lamps, or UV light sources.
6. Willingness to apply study provided sunscreen (Neocutis Micro-Day Rejuvenating Cream) daily until study exit to help limit sun exposure.
7. Willingness to avoid or periodically stop use of Sunless Tanners (washout period of two weeks prior to each study visit is required).
8. Understands and accepts the obligation not to undergo any other procedures in the areas to be treated through the follow-up period.
9. Willingness to avoid non-emergent dental procedures in the 3 weeks prior/post treatment.

10. Willingness and ability to comply with protocol requirements, including returning for follow-up visits and abstaining from exclusionary procedures for the duration of the study.
11. Subjects of childbearing potential must have a negative urine pregnancy test result and must not be lactating at the Screening Visit and be willing and able to use an acceptable method of birth control (e.g. barrier methods used with a spermicidal agent, hormonal methods, IUD, surgical sterilization, abstinence) during the study. Women will not be considered of childbearing potential if one of the following conditions is documented on the medical history:
 - a. Postmenopausal for at least 12 months prior to study;
 - b. Without a uterus and/or both ovaries; or
 - c. Bilateral tubal ligation at least six months prior to study enrollment.
12. Absence of physical or psychological conditions unacceptable to the investigator.
13. Willingness to refrain from use of aspirin, Ibuprofen, Naproxen or any other NSAID prior to each study treatment and chronic use during the entire post-treatment study period. Washout period, if chronic user, for 4 weeks prior to the study treatment. After study treatment is completed, limited acute NSAID use, i.e., a maximum of 2-3 doses in any 2 week period, is allowed if needed.
14. Willingness and ability to provide written consent for study-required photography and adherence to photography procedures (i.e., removal of jewelry and makeup).

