4.4 SCREEN FAILURES

A screen failure subject is one from whom informed consent is obtained and is documented in writing (i.e., subject signs an Informed Consent Form), but who does not receive a study treatment because of failure to meet all of the eligibility criteria. Screen failure subjects will be included in the total number of subjects enrolled (i.e., all subjects consented), but not counted towards the total subjects treated.

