5.1.2 PRE-TREATMENT MEDICATIONS

For this protocol, pre-treatment medications will be restricted to Ibuprofen (800mg) taken by all subjects at least 60 minutes but not more than two hours prior to study treatment.

[figure not shown]

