5.2 SAFETY VARIABLES

Prior to treatment, the subject's medical history will be reviewed, a urine pregnancy test will be performed (if applicable), and a physical examination will be conducted. During Ultherapy[®] treatment, the subject's pain levels will be monitored using a validated Numeric Rating Scale (Attachment D). Average pain scores should be obtained following each region treated and for each transducer used during treatment. The average pain score for the entire region treated by each transducer will be recorded. A script will be used for collecting pain scores.

At each subsequent visit, the subject will be queried about adverse events and changes in concomitant medications, and the treatment area will be visually examined. A second pregnancy screening test will be performed at the 365-day follow-up visit.

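### Exclusion 6 names only ibuprofen, so subjects whom Section 8.1 says should not receive NSAIDs can be enrolled and given ibuprofen 800 mg under Section 5.1.2

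*Combined protocol and SAP*

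**What the plan says.** Four parts of the protocol bear on this.

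- **Section 8.1 (Potential Risks)** states a contraindication for the whole drug class: "NSAIDs (e.g., Ibuprofen) should not be given to patients who have experienced asthma, urticaria, or allergic-type reactions after taking aspirin or other NSAIDs". Soon afterwards it says "These risks will be minimized or reduced by monitoring the subject during the treatment".
- **Exclusion 6**, worded identically in the synopsis and in Section 4.3.2, reads "Known allergy or sensitivity to Ibuprofen". Aspirin and other NSAIDs are not mentioned.
- **Section 5.1.2 (Pre-Treatment Medications)** says that "pre-treatment medications will be restricted to Ibuprofen (800mg) taken by all subjects at least 60 minutes but not more than two hours prior" to treatment. It gives no exemption and no alternative drug.
- **Section 6.3 (Analysis Populations)** counts any pain premedication other than ibuprofen as a major protocol violation.

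Some general provisions could also apply. Inclusion 10 asks for "Willingness and ability to comply with protocol requirements". Inclusion 12 requires "Absence of physical or psychological conditions unacceptable to the investigator". Section 5.2 provides that, before treatment, the subject's "medical history will be reviewed, a urine pregnancy test will be performed (if applicable), and a physical examination will be conducted". Inclusion 2 asks for good health. Inclusion 13 names the NSAID class, but only to restrict use and set a washout.

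**The concern.** The protocol identifies a group who should not be given its only permitted premedication, and then does not turn that into an eligibility rule. A site that works through the listed criteria and follows Section 5.1.2 as written could give 800 mg of ibuprofen to someone with a history of urticaria or asthma after aspirin. An allergic-type reaction to an NSAID can be serious for the individual. The study treatment is cosmetic, so a participant has little to gain that would justify an avoidable contraindicated dose. With up to eight sites, reliance on individual judgement also invites inconsistent screening.

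**Working it through.** No formula underlies this point and the plan states no figure to reproduce. The check is a comparison of texts, followed by a rough count under a stated assumption.

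**1. Compare the two groups.** Section 8.1 covers anyone with past asthma, urticaria or an allergic-type reaction after aspirin or another NSAID. Exclusion 6 covers known allergy or sensitivity to ibuprofen. The first group contains people who are not in the second, for example someone with hives after naproxen who has never knowingly reacted to ibuprofen.

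**2. Look for another criterion that catches them.** Inclusions 2, 10 and 12 and the history review in Section 5.2 are generic: none names NSAID reactions and none obliges the site to refuse the subject. Inclusion 13 shows that the protocol spells out the class when it means the class, but it governs current use, not past reactions. No listed criterion closes the gap.

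**3. Follow such a subject forward.** Once enrolled, the subject falls under the instruction in Section 5.1.2, which covers all subjects. The investigator then has three options:

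| Action | Consequence under the protocol |
|---|---|
| Give ibuprofen 800 mg | Contrary to the warning in 8.1 |
| Give a different analgesic | Contrary to 5.1.2, and a major violation under 6.3 |
| Give nothing | Departs from 5.1.2; Section 5.6 expects the study to run as described except in an emergency (6.3 does not list omission as a major violation) |

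No option satisfies every section, so the conflict has to be resolved at screening.

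**4. Check the timing of the stated mitigation.** Monitoring takes place during treatment. Under Section 5.1.2, treatment starts 60 minutes to two hours after the dose. Monitoring therefore cannot prevent the exposure.

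**5. Rough size.** The documents give neither the prevalence of aspirin or NSAID reactions nor the reaction rate on ibuprofen. Assume a prevalence of 0.5% to 2% among otherwise eligible candidates:

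- People concerned among 260 randomised: 260 × 0.005 = 1.3; 260 × 0.02 = 5.2.
- Extra candidates needed to keep 260 randomised once they are excluded: 260 / 0.995 − 260 = 1.3; 260 / 0.98 − 260 = 5.3.

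These figures count people whom the criterion should identify, not adverse events. They are on the high side for the assumed range, because anyone who also has a known ibuprofen reaction already meets Exclusion 6 and has not been subtracted.

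**The case against.** The strongest reply is that the contraindication is not missing. Section 8.1 is current protocol text, it is specific, and an investigator who has read the whole document has been told not to give ibuprofen to these people. On this view the instruction is merely in the wrong section. A clinician might also read sensitivity to ibuprofen as including cross-reactivity with other NSAIDs, and the NSAID conversation required by Inclusion 13 is a natural moment for such a history to come up. This has some force: a careful investigator would probably keep such a subject out. It does not remove the conflict, because Section 5.1.2 applies to all subjects and the eligibility list, which sites work from, says nothing about the wider class.

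The monitoring sentence in Section 8.1 can fairly be read as concerning mainly the ultrasound, since it goes on to mention the skin's response and stopping a treatment that is not tolerated. The timing argument is therefore secondary, and the finding stands without it.

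The prevalence range is an assumption and carries no evidential weight. The mismatch between the sections does not depend on it.

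A less restrictive remedy exists: exempt these subjects from premedication in Section 5.1.2, since the hazard is the drug and not the device. That is possible, but pain score is a compared secondary endpoint (Section 5.3.2, item 7), and unpremedicated subjects would complicate that comparison. Exclusion is cleaner.

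Finally, the consent form and case report forms are not part of the text examined, so site-level screening questions about NSAID reactions cannot be ruled out. They would not change the wording of Exclusion 6 or Section 5.1.2.

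**Conclusion.** The concern holds. Exclusion 6 is narrower than the warning in Section 8.1, and following the listed criteria and then Section 5.1.2 can lead to a dose that the protocol itself says should not be given. The conclusion rests on the wording alone. The number of people concerned is probably small, about 1 to 5 of 260 if the prevalence is 0.5% to 2%, and that range is assumed. The consequence for an individual could be serious and the correction is cheap, so the sponsor should make it. Type I error, power, the sample size and the primary analysis are untouched.

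**What to change.** Reword Exclusion 6 in place, in both the synopsis and Section 4.3.2, for example: *Known allergy or sensitivity to ibuprofen, or any history of asthma, urticaria or allergic-type reaction to aspirin or another NSAID.*

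Sections 5.1.2 and 8.1 then agree with the eligibility list and need no change. Rewording the existing item, instead of adding one, preserves the exclusion numbers cited in Section 6.3. Exclusion 6 is not among the major criteria listed there, so the per-protocol definition stays the same.

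The cost is one sentence in two places. Because the change affects eligibility it is not administrative, so under Section 14 sites must wait for IRB approval before applying it. A few otherwise eligible candidates will be lost at screening. Under Section 4.4, screen failures are included in the enrolled total "but not counted towards the total subjects treated", so the targets of 260 randomised and 109 evaluable per group stand.

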8.2 MINIMIZATION OF POTENTIAL RISKS

The risks listed above are minimized by performing two to three treatment line exposures and noting the subject's sensation and inflammatory response. Risks have also been minimized by prior testing (including preclinical, animal, and clinical) conducted with the Ulthera[®] System.

8.3 POTENTIAL BENEFITS

There is a potential benefit to participants of this study who are seeking lifting and tightening of skin laxity. Results of the study may contribute to further development of the ultrasound-based, non-invasive tissue-tightening procedure.

8.4 JUSTIFICATION FOR THE CLINICAL STUDY

The current clinical study is justified based on the previous safe clinical experience with the Ulthera[®] System for cosmetic applications to facial skin, and the efficacy in related cosmetic applications for skin tightening. The current clinical plan is expected to result in lifting and tightening of the skin, wrinkle reduction, and achievement of a positive clinical outcome.

9. DEVICE MANAGEMENT

9.1 PACKAGING

On a site-specific basis, the Ulthera[®] System will be shipped in a hard case designed to protect the system during delivery. Upon arrival at the clinical site, the Ulthera[®] System will be set up by Ulthera personnel for pre-study testing to ensure that the system is functioning properly.

9.2 STORAGE

Shipping and storage conditions include:

Shipping and Storage, System without Transducers

[REDACTED]

Shipping and Storage, with Transducers

[REDACTED]

9.3 ACCOUNTABILITY

The investigator, or designee, must maintain an inventory record of study devices received, used for treatment, and returned to the Sponsor to ensure that the investigational device will not be dispensed to any person who is not a subject under the terms and conditions set forth in this protocol. There will be 100% accountability for all investigational Ulthera[®] Systems and transducers.

10. REGULATORY AND ETHICAL REQUIREMENTS

This clinical study will be conducted in accordance with the Protection of Human Subjects Regulations, including Subpart B Informed Consent of Human Subjects (21 CFR Part 50); the Institutional Review Board Regulations (21 CFR Part 56); the Financial Disclosure by Clinical Investigators Regulations (21 CFR Part 54); and the Investigational Device Exemptions Regulations (21 CFR Part 812).

10.1 INFORMED CONSENT

Informed consent will be obtained from all subjects prior to study participation.

10.2 INSTITUTIONAL REVIEW BOARD

Prior to initiation of any study procedures, the protocol, informed consent, and operators manual will be submitted to a duly constituted IRB for review and approval. In addition, any amendments to the protocol or Informed Consent Form will be reviewed and approved by the IRB. The Sponsor must receive a letter documenting IRB approval at the clinical site prior to the initiation of the study.

The investigator is responsible for providing the appropriate reports to its reviewing IRB during the course of the clinical study. These reports will include:

- Informing the IRB of the study progress periodically as required, but at least annually;
- Reporting any unanticipated adverse device effects within 10 working days of first learning of the event;
- Reporting any deviations from the clinical protocol to protect the life or well-being of a subject in the case of an emergency within five working days after the emergency occurred;
- Reporting the use of the device without obtaining informed consent from a subject within five working days of the event; and
- Providing any other reports requested by the IRB.

The IRB must be notified of study completion within 30 days of the final visit of the last subject and should be provided with a summary of the results of the study by the investigator.

